10.1.1. Deaths

The following death summaries will be generated in a summary table or listed in a by-subject data listing:

- Number and percentage of subjects who died by treatment group for the Safety Analysis Population
- Death in non-randomized subjects or randomized but not treated subjects
- TEAEs leading to death (death as an outcome on the AE eCRF page as reported by the investigator) by primary SOC and PT showing number and percentage of subjects

10.1.2. Pregnancy

The following pregnancy summaries will be generated:

- Number of participants who became pregnant summarized by treatment group
- Outcomes of the pregnancies and analysis of the outcomes
- TEAE experienced during the pregnancy by primary SOC and PT showing the number and percent of participants

10.1.3. Overdose

Overdose is defined per protocol as taking more capsules of study drug than directed. The following overdose information will be provided:

- Number of subjects who experienced overdose summarized by treatment group
- Listing of the cause and occurrence of the overdose
- Summary of TEAEs as symptomatic response to overdose by primary SOC and PT showing the number and percent of subjects

10.2. 12-lead Electrocardiogram

12-lead electrocardiogram (ECG) data will be summarized for all subjects in the Safety Analysis Population, for subjects without pacing, and for subjects with baseline QRS <120 ms versus ≥ 120 ms in the analyses described in this section.

The RR, PR, QRS, and QT intervals will be measured and read by a central laboratory. HR will be calculated as $60/(RR \times 1000)$ (with RR expressed in msec) and rounded to the nearest integer.

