#### 12.4.8.2 12-lead Electrocardiogram

The RR, PR, QRS, and QT intervals will be measured and read by a central laboratory. HR will be calculated as  $60 / (\text{RR} \times 1000)$  (with RR expressed in msec) and rounded to the nearest integer.

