10.2.1. Correction for Heart Rate

Corrected QT interval (QTc) will be calculated using the manually over-read QT values. Each individual ECG QT value will be corrected for HR. The measured QT data will be corrected for HR using Fridericia-corrected QT interval (QTcF) as per the following formulae/method (with QT, RR, and QTc expressed in msec):

Fridericia's correction:

$$QTcF = \frac{QT}{(RR/1000)^{(1/3)}}$$

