10.2.2. ECG Numeric Variables

HR, PR, QRS, and QTcF and changes from baseline will be summarized by treatment group using descriptive statistics. The change from baseline of these ECG parameters at each time point will be listed for each subject.

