10.2.3. Categorical Analysis

The number and percentage of subjects with maximum post-dose QTcF values > 450 msec, > 480 msec, > 500 msec, > 520 msec, and > 550 msec will be summarized by treatment group. Participants with QTcF values > 500 msec will be listed along with corresponding baseline values, Δ QTcF, and baseline and treatment HR. The number and percentage of subjects with QTcF increase from baseline > 30 msec and > 60 msec will be summarized by treatment group.

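### The ECG heart-rate formula in both documents multiplies RR by 1000 where it should divide, so every heart rate rounds to 0 bpm

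*SAP*

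**What the plan says.** SAP section 10.2 (12-lead Electrocardiogram) first says which quantities come from the ECG reading: "The RR, PR, QRS, and QT intervals will be measured and read by a central laboratory". Heart rate is not among them; it is derived from RR: "HR will be calculated as $60/(RR \times 1000)$ (with RR expressed in msec) and rounded to the nearest integer".

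Protocol section 12.4.8.2 prints the same expression and the same unit and rounding rule ("with RR expressed in msec) and rounded to the nearest integer").

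The derived heart rate is then used in two places:

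- SAP 10.2.2: "HR, PR, QRS, and QTcF and changes from baseline will be summarized by treatment group using descriptive statistics". Changes from baseline are also listed by subject and time point. Under SAP 10.2 the ECG summaries are produced for all subjects, for subjects without pacing, and by baseline QRS below 120 ms or not. The Protocol plans similar heart-rate summaries.
- SAP 10.2.3: participants with QTcF above 500 msec are listed with their QTcF values "and baseline and treatment HR". The Protocol has the same kind of listing, with a threshold of 520 msec.

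The formula that follows directly, Fridericia's correction in SAP 10.2.1, uses the same unit ("with QT, RR, and QTc expressed in msec") but divides RR by 1000 before taking the cube root. The Protocol's version of that formula does the same.

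**The concern.** Two adjacent formulas take the same variable in the same unit and convert it in opposite directions. Dividing milliseconds by 1000 gives seconds, which is what a rate per 60 seconds needs. Multiplying by 1000 gives microseconds, and 60 divided by microseconds is not beats per minute.

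At stake are the planned ECG heart-rate outputs. If the derivation is programmed as specified, every heart rate and every change from baseline is zero. The heart rates listed beside prolonged QTcF values, which help a reader judge a rate-corrected interval, would be zero as well if taken from this derivation. If a programmer quietly uses the right formula, the output departs from the SAP without a record, and an independent programmer working from the specification would not reproduce it.

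**Working it through.** **Inputs**

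- Printed formula: HR = 60/(RR × 1000), from SAP 10.2 and Protocol 12.4.8.2.
- Unit of RR: milliseconds, in both documents.
- Rounding: nearest integer, in both documents.
- RR values: the documents give none. Values from 300 to 2000 ms (200 to 30 bpm) are assumed for illustration.

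Neither document gives a worked heart rate, so there is no stated figure to reproduce. The check evaluates the formula as printed and compares it with the unit conversion.

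**Formulas**

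- As printed: 60/(RR × 1000) = 0.06/RR.
- Beats per minute with RR in ms: 60/(RR/1000) = 60000/RR.
- Ratio: (60000/RR)/(0.06/RR) = 1,000,000, whatever the RR.

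**Results**

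| RR (ms) | As printed | Rounded | 60000/RR (bpm) |
|---|---|---|---|
| 300 | 0.0002 | 0 | 200 |
| 600 | 0.0001 | 0 | 100 |
| 800 | 0.000075 | 0 | 75 |
| 1000 | 0.00006 | 0 | 60 |
| 1200 | 0.00005 | 0 | 50 |
| 2000 | 0.00003 | 0 | 30 |

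**Does the assumed RR range matter?** The printed formula reaches 0.5, the least that could round to 1, only when RR ≤ 60/(1000 × 0.5) = 0.12 ms. No heartbeat interval is that short, so the result does not depend on the range chosen.

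**Could the unit be the slip instead?** If RR were in seconds, RR = 1 s would give 60/(1 × 1000) = 0.06, which is too small by a factor of 1000 and still rounds to 0. Changing the unit alone does not rescue the formula.

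**Could it be a PDF reading error?** This is unlikely. The same expression appears in two separate documents, and the division by 1000 in the neighbouring QTcF formula was read correctly in both.

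**The case against.** The arithmetic is not in dispute. The case on the other side is about weight.

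First, the error is conspicuous. A table showing 0 bpm for everyone would be caught at first output, whereas the dangerous formula errors are those that give plausible wrong numbers. The intended formula is also obvious: a misplaced bracket, with (60/RR) × 1000 meant, or a multiplication sign typed for a division sign, both lead to 60000/RR.

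Second, little depends on it:

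- QTcF is computed from QT and RR directly, so QTcF values, their categories and the concentration-QTcF model are unaffected.
- The ECG criteria for temporary discontinuation in Protocol 7.3.2 use QTcF and QRS, not derived heart rate.
- The primary and secondary efficacy endpoints do not use ECG heart rate.
- Safety analyses are descriptive, so no test, alpha or power is involved.
- Heart rate is also summarized from vital signs (SAP 10.4), and maximum heart rate from 48-hour monitoring (SAP 10.5).

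Third, Protocol 12.4 describes its analyses as an outline and leaves the detail to the SAP, so correcting the SAP alone would settle the programming.

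All of this stands as a limit on the consequence. It does not make the formula right. A derivation in a SAP should be executable as written, and this one is not. Easy detection is a reason to correct it quickly, not to leave it in two controlled documents.

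**Conclusion.** The heart-rate formula is wrong as written in both documents. It is too small by a factor of exactly 1,000,000 and rounds to 0 bpm for every physiological RR interval. No other text in either document corrects it, and the adjacent QTcF formula contradicts it.

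The effect is limited to ECG-derived heart rate: its summaries, its changes from baseline, and any derived heart rate shown in the prolonged-QTcF listing. The conclusion rests only on the printed formula, the stated unit and the rounding rule; the RR values used above are illustrative. The formula should be corrected, but the error does not threaten the trial's efficacy conclusions or its QTcF assessment.

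**What to change.** In SAP 10.2 and Protocol 12.4.8.2, replace the expression with HR = 60/(RR/1000) = 60000/RR, with RR in milliseconds, rounded to the nearest integer. This brings the conversion into line with the QTcF formula beside it.

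The cost is one line in each document, with no change to data collection or to any other analysis. The SAP correction is the one that governs programming. For the Protocol, section 14.4 allows an Administrative Letter for obvious errors and inconsistencies, with ethics committee communication or approval where local rules require it, so a substantial amendment should not be needed.

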10.2.1. Correction for Heart Rate

Corrected QT interval (QTc) will be calculated using the manually over-read QT values. Each individual ECG QT value will be corrected for HR. The measured QT data will be corrected for HR using Fridericia-corrected QT interval (QTcF) as per the following formulae/method (with QT, RR, and QTc expressed in msec):

Fridericia's correction:

$$QTcF = \frac{QT}{(RR/1000)^{(1/3)}}$$

10.2.2. ECG Numeric Variables

HR, PR, QRS, and QTcF and changes from baseline will be summarized by treatment group using descriptive statistics. The change from baseline of these ECG parameters at each time point will be listed for each subject.

10.2.3. Categorical Analysis

The number and percentage of subjects with maximum post-dose QTcF values > 450 msec, > 480 msec, > 500 msec, > 520 msec, and > 550 msec will be summarized by treatment group. Participants with QTcF values > 500 msec will be listed along with corresponding baseline values, Δ QTcF, and baseline and treatment HR. The number and percentage of subjects with QTcF increase from baseline > 30 msec and > 60 msec will be summarized by treatment group.

10.2.4. Morphology Findings

ECG morphologies for each subject will be listed.

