##### *Morphology Findings*

New ECG morphologies for each participant not present on any ECG at baseline for that participant will be summarized for all observation time points combined.

The number and percentage of participants having T-wave morphology changes and/or the occurrence of abnormal U-waves that represent the appearance or worsening of the morphological abnormality from baseline will be reported.

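### SAP 10.2.4 replaces the protocol's baseline-referenced summary of new or worsened ECG morphology with a per-subject listing, and no visible SAP analysis supplies the missing count.

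*SAP*

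**What the plan says.** Protocol 12.4.8.2, under Morphology Findings, makes two commitments. The first is: "New ECG morphologies for each participant not present on any ECG at baseline for that participant will be summarized for all observation time points combined". A second commitment concerns repolarization: "The number and percentage of participants having T-wave morphology changes and/or the occurrence of abnormal U-waves" are to be reported, limited to changes "that represent the appearance or worsening of the morphological abnormality from baseline will be reported". Both are summaries, and both are defined relative to baseline.

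SAP 10.2.4, under the same heading, reads in full: "ECG morphologies for each subject will be listed". It mentions no count, percentage, baseline rule or treatment group.

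The neighbouring SAP subsections are written differently. SAP 10.2.2 says "HR, PR, QRS, and QTcF and changes from baseline will be summarized by treatment group using descriptive statistics", and SAP 10.2.3 says "The number and percentage of subjects with QTcF increase from baseline > 30 msec and > 60 msec will be summarized by treatment group".

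**The concern.** A listing shows what each subject's ECG looked like. It does not say how many subjects developed something they did not have before dosing. The distinction matters in this population because every participant has left ventricular hypertrophy by inclusion criterion 5, so some ECG abnormality before treatment is plausible. That is an assumption, since the documents give no rate. If it holds, pre-existing and new findings would sit together in the listing unless the new ones are flagged.

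Repolarization is also something this trial watches: QTcF prolongation is one of the criteria for temporary discontinuation in Protocol 7.3.2. At stake is whether the study report would contain a planned count of new T-wave or U-wave changes, or leave the reader to derive one from individual records.

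**Working it through.** No figure in the plan bears on this point and no arithmetic applies. The check is a side-by-side reading, followed by a search of the visible SAP for a substitute.

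**Step 1: compare the two Morphology Findings sections.**

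| Element | Protocol 12.4.8.2 | SAP 10.2.4 |
|---|---|---|
| Morphologies absent from all baseline ECGs | Summarized, time points pooled | Not mentioned |
| T-wave and U-wave changes | Counts and percentages | Not mentioned |
| Restriction to appearance or worsening | Yes | No |
| Treatment group named | No | No |
| Per-subject listing | Not mentioned | Yes |

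Two specified summaries become none, and one listing is added.

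**Step 2: look for the summary elsewhere in the visible SAP.**

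- *Section 6, general considerations.* Descriptive summaries are by treatment group as a default. This governs layout. It does not create a morphology table or define a new or worsened morphology.
- *Section 10.2, opening paragraph.* It says "12-lead electrocardiogram (ECG) data will be summarized for all subjects in the Safety Analysis Population" and for certain subgroups, but ties this to the analyses described in that section. For morphology, the only analysis described is the listing.
- *Sections 10.2.2, 10.2.3 and 10.2.5.* These cover heart rate, intervals, QTcF categories and the concentration-QTcF model. None covers T-wave or U-wave morphology.
- *Section 10.1, adverse events.* Treatment-emergent events are tabulated by system organ class, preferred term and treatment group. A morphology change appears only if it was recorded as an adverse event.
- *Section 10.6, other safety analysis.* It counts subjects meeting discontinuation or interruption criteria. The ECG criterion visible in Protocol 7.3.2 is based on QTcF, with a threshold that depends on QRS width, and not on morphology.

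**Step 3: test the adverse event route.** Protocol 9.3 records abnormal findings as adverse events when the investigator judges them clinically important, and Protocol 11.1.1 sends clinically important new or worsening test abnormalities to the adverse event form. Protocol 11.1.1.1 excludes abnormal safety assessments associated with the disease under study unless they are judged more severe than expected. A T-wave change that an investigator attributes to hypertrophic cardiomyopathy at its expected severity can therefore stay out of the adverse event tables. The route captures some morphology changes, not all.

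**Step 4: check whether the change is explained.** SAP Section 14 is the place for departures from the protocol's analyses. In this copy it shows a heading and no text, so neither a stated reason nor its absence can be established.

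**The case against.** The strongest opposing case has four parts.

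*The protocol is an outline.* Protocol 12.4 says so and leaves full detail to the SAP, so a difference is not in itself a fault. That stands as a general rule. Here, however, the SAP adds no detail to the planned summary. It removes a specified safety output, and any reason for doing so is not visible.

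*The safety question is largely covered.* For QTcF the SAP goes further than the protocol. It adds categories above 450 and 480 msec, lowers the threshold for listing subjects from above 520 to above 500 msec, and adds analyses without paced subjects and by baseline QRS width. It also counts subjects meeting each interruption criterion by treatment. This stands, and it keeps the point small. A reader might infer that repolarization safety goes unexamined, and the documents do not support that.

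*New changes can still be found and compared.* A reader might infer that treatment-emergent morphology changes will never be separated from pre-existing ones or compared between arms. That is too strong. Clinically important changes can appear in the adverse event tables by treatment group. Nothing in SAP 10.2.4 excludes baseline ECGs from the listing, so a before-and-after reading is possible, and parts of the SAP are redacted. What can be said is that no visible planned analysis gives the count.

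*The protocol does not promise counts by arm.* This is correct. Its morphology text names no treatment group, and the adjacent QTcF text tabulates for all participants. Presentation by group is an inference from the two-arm comparison described in Protocol 12.2, supported by the practice in SAP 10.2.2 and 10.2.3. It is a sensible way to restore the table but not a quoted commitment.

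A practical objection also stands. The documents say the central laboratory reads the RR, PR, QRS and QT intervals. No visible text says it codes or grades T-wave or U-wave morphology, or defines worsening.

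**Conclusion.** The discrepancy is real and minor. The protocol specifies a baseline-referenced summary of ECG morphology, the SAP substitutes a listing, and no visible SAP analysis fills the gap. The adverse event tables are a partial substitute only.

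The size is one missing descriptive table. No numerical effect on the trial's conclusions can be derived, because the documents give no rate of morphology change in either arm. SAP Section 10 plans no hypothesis tests for safety, so producing the table, even late, raises no error-control issue.

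The conclusion assumes that redacted SAP text does not contain the summary. It does not extend to calling the change undeclared, since the content of Section 14 cannot be seen.

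**What to change.** In SAP 10.2.4, restore the protocol's summary as one descriptive table on the Safety Analysis Population, by treatment group in line with SAP 10.2.2 and 10.2.3. With all post-dose time points combined, it should give the number and percentage of subjects with:

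- a morphology absent from all of that subject's baseline ECGs;
- a T-wave or U-wave abnormality that newly appeared;
- a T-wave or U-wave abnormality that worsened, if the central reading grades these findings, with worsening defined in the SAP.

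If no grading exists, the table can be limited to new appearance, and the SAP should say so. The SAP should also name the ECGs that count as baseline. Protocol Table 1 schedules a Day 1 ECG, while Protocol 9.3.3 excepts Day 1, and these passages must be reconciled.

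Keep the listing and flag the treatment-emergent findings in it. If the summary was dropped on purpose, give the reason in Section 14.

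The cost is one extra table and a short set of definitions. The listing already requires morphology data in some form, but whether those data are coded well enough to tabulate should be confirmed with the central laboratory first. The change concerns reporting only and touches no dosing, stopping or management rule.

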10.2.5. Concentration-QTcF Analyses

The relationship between mavacamten concentration and Δ QTcF will first be evaluated by a scatterplot of time-matched concentration and Δ QTcF data. A linear mixed model will be used to estimate the slope and 95% CI of the concentration-QTcF relationship. For the linear mixed-effects model, the fixed effects can include but not limited to concentration and sex, and subject will be included as a random effect. Compound symmetry will be implemented for the variance-covariance structure.

10.3. Safety Laboratory Data

Safety laboratory data will be summarized by treatment group and visit using descriptive statistics.

Shift tables reflecting changes from baseline (ie, normal to low, high, etc.) will be presented in lieu of descriptive statistics of changes from baseline. Listings of laboratory values will be generated and the results that are out of the reference range will be flagged.

10.3.1. Potential Drug-induced Liver Injury

The liver function tests, namely alanine aminotransferase (ALT), aspartate aminotransferase (AST), alkaline phosphatase (ALP), and total bilirubin (TBL) are used to assess possible drug-induced liver injury (DILI).

A graph of distribution of peak values of ALT versus peak values of TBL will be presented. ALT and TBL values will be presented on a logarithmic scale. The graph will be divided into 4 quadrants with a vertical line corresponding to $3 \times$ the upper limit of normal (ULN) for ALT and a horizontal line corresponding to $2 \times$ ULN for TBL.

The number and percentage of subjects with elevated liver function tests (based on safety laboratory data) during the TEAE period will be summarized by categories of elevation ($>3 \times \text{ULN}$, $>5 \times \text{ULN}$, $>10 \times \text{ULN}$, $>20 \times \text{ULN}$ for ALT and AST, $>1.5 \times \text{ULN}$ for ALP, and $>1.5 \times \text{ULN}$ and $>2 \times \text{ULN}$ for TBL), along with the following categories of normalization (i.e. return to $\leq 1 \times \text{ULN}$, or return to baseline if baseline $> \text{ULN}$): never normalized, normalized after permanent discontinuation of study drug, normalized during treatment period and elevated after permanent discontinuation of study drug. Potential Hy's law cases will be investigated by summarizing the number of subjects with elevated ALT or AST ($>3 \times \text{ULN}$) and with elevated total bilirubin ($>2 \times \text{ULN}$) where transaminase elevation coincides with or precedes BILI elevation.

10.4. Vital Signs Data

Vital signs, including heart rate (HR), systolic blood pressure, and diastolic blood pressure, values and changes from baseline will be summarized by treatment group and visit using descriptive statistics.

10.5. Cardiac Rhythm Monitoring (Including Holter Monitor)

The summary statistics of maximum HR, atrial fibrillation (Afib) percentage time, and VT (sustained or non-sustained) frequency will be calculated for each cumulative 48-hour Holter monitoring period and summarized by treatment group and visit. For each of the cardiac event type (Afib and VT), the number of subjects with ≥ 1 occurrence will be summarized. The percentage of time in Afib and number of VT episodes per subject will also be summarized. Additional parameters (eg, supraventricular tachycardia, premature ventricular contractions, pauses) may be summarized and analyzed as appropriate.

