### **5.3 Exclusion Criteria**

A participant who meets any of the following criteria will be excluded from the study.

1. Previously participated in a clinical study with mavacamten
2. Hypersensitivity to any of the components of the mavacamten formulation
3. Participated in a clinical trial in which the participant received any investigational drug (or is currently using an investigational device) within 30 days prior to Screening, or at least 5 times the respective elimination half-life (whichever is longer)
4. Known infiltrative or storage disorder causing cardiac hypertrophy that mimics oHCM, such as Fabry disease, amyloidosis, or Noonan syndrome with LV hypertrophy
5. Has any medical condition that precludes upright exercise stress testing
6. Has a history of syncope within 6 months prior to screening or history of sustained ventricular tachyarrhythmia with exercise within 6 months prior to Screening
7. Has a history of resuscitated sudden cardiac arrest (at any time) or known history of appropriate ICD discharge/shock for life-threatening ventricular arrhythmia within 6 months prior to Screening (Note: history of anti-tachycardia pacing (ATP) within 6 months or ever is allowed)
8. Has paroxysmal, intermittent atrial fibrillation with atrial fibrillation present per the investigator's evaluation of the participant's ECG at the time of Screening
9. Has persistent or permanent atrial fibrillation not on anticoagulation for at least 4 weeks prior to Screening and/or not adequately rate controlled within 6 months of Screening (Note – patients with persistent or permanent atrial fibrillation who are anticoagulated and adequately rate-controlled are allowed)
10. Current treatment (within 14 days prior to Screening) or planned treatment during the study with disopyramide or ranolazine
11. Current treatment (within 14 days prior to Screening) or planned treatment during the study with a combination of  $\beta$ -blockers and verapamil or a combination of  $\beta$ -blockers and diltiazem
12. For individuals on  $\beta$ -blockers, verapamil, or diltiazem, any dose adjustment of that medication <14 days prior to Screening or an anticipated change in treatment regimen using these medications during the study
13. Has been successfully treated with invasive septal reduction (surgical myectomy or percutaneous ASA) within 6 months prior to Screening or plans to have either of these treatments during the study (note: individuals with myectomy or percutaneous ASA

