## 12.2.5 Safety Endpoints

- Incidence of major adverse cardiac events (death, stroke, acute myocardial infarction)
- Incidence of hospitalizations (both cardiovascular (CV) and non-CV))
- Incidence of heart failure (HF) events, (includes HF hospitalizations and urgent emergency room (ER)/outpatient (OP) visits for HF)
- Incidence of atrial fibrillation/flutter (new from screening)
- Incidence of ICD therapy and resuscitated cardiac arrest
- Incidence of Ventricular tachyarrhythmias (includes VT, VF, and Torsades de Pointe)
- Incidence of syncope and seizures
- Frequency and severity of treatment-emergent adverse events (TEAE), treatment-emergent SAEs, and laboratory abnormalities (including trends in NT-proBNP)

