6. GENERAL STATISTICAL CONSIDERATIONS

The primary analysis will be conducted through the 30-week treatment period. Data collected through this time point will be cleaned and locked prior to conducting the primary analysis.

Once all participants have completed their Week 38/end of study (EOS) visit, all data will be cleaned and locked, and analyses using this data will be used to inform study objectives relating to follow-up safety and reversibility of drug effect.

SAS® version 9.4 or higher will be used for statistical analyses, tabulations, and graphical presentations.

In general, descriptive summaries will be presented by treatment group (placebo and mavacamten) for values at each visit. The descriptive summary for continuous variables will also be provided for the change from baseline and, if appropriate, for the change from week 30 to week 38. Summaries of continuous variables will include the number of subjects (N), mean, standard deviation (SD), median, Q1, Q3, minimum, and maximum. For variables with highly skewed distribution (e.g. log-normal distribution), geometric mean and %CV will also be reported in descriptive summaries. Inferential analysis for those variables may be performed after log-transformation as deemed appropriate. Descriptive summaries for categorical variables will include the number and percentage of subjects. Unless otherwise stated, denominators for percentages will be the number of subjects in the analysis population.

Between-group comparisons will focus on the comparative performance of mavacamten versus placebo. All statistical tests will be conducted at a 2-sided significance level of 0.05.

In general, baseline is defined as the last nonmissing value on or before the first dose date and time (as applicable). For certain data types (eg, accelerometer, PROs, cardiac rhythm monitoring, etc.), special considerations may be required. Refer to the specific data section for details.

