10. SAFETY ANALYSES

All safety analyses will be performed on the Safety Analysis Population using the following common rules:

- The baseline value is defined generally as the last available value before the first administration of study drug.
- The analysis of the safety variables will be descriptive and no hypothesis testing is planned.

The safety analyses will focus on the treatment emergent period, which is defined as the time from the first administration of study drug to the last administration of study drug plus 56 days.

A by-subject listing of all AEs will be provided.

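### The Holter count of subjects with atrial fibrillation in SAP 10.5 cannot separate new AF from AF present at entry

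*SAP*

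**What the plan says.** - **Who may enter.** Exclusion 9 (Protocol 5.3) notes that "patients with persistent or permanent atrial fibrillation who are anticoagulated and adequately rate-controlled are allowed". Exclusion 8 removes paroxysmal AF only if AF is present on the Screening ECG. Some participants will therefore have AF at entry by design.
- **The safety endpoint.** Protocol 12.2.5 lists AF as an endpoint only when it is new ("Incidence of atrial fibrillation/flutter (new from screening"). Protocol 9.3 puts it on the list for the Clinical Event Adjudication Committee.
- **The Holter summary.** SAP 10.5 states: "For each of the cardiac event type (Afib and VT), the number of subjects with" at least one occurrence will be summarized. It adds: "The percentage of time in Afib and number of VT episodes per subject will also be summarized". It neither defines new AF nor splits by baseline rhythm.
- **Population and denominator.** SAP 10: "All safety analyses will be performed on the Safety Analysis Population". SAP 6: "Unless otherwise stated, denominators for percentages will be the number of subjects in the analysis population". Section 10.5 states nothing different.
- **Baseline.** SAP 6: "For certain data types (eg, accelerometer, PROs, cardiac rhythm monitoring, etc.), special considerations may be required. Refer to the specific data section for details". Section 10.5 contains no baseline rule.
- **Timing.** Protocol Table 1 and its footnote on the cardiac monitoring device schedule recordings at Screening, Week 12 and Week 26, so baseline rhythm is recorded.

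**The concern.** A participant in permanent AF will show AF on essentially every recording, whatever the treatment, and cannot develop new AF. Counting that participant as a subject with at least one occurrence adds a constant to both arms and pulls the ratio between arms towards 1.

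AF at entry is not a stratification factor. The number of such participants can also differ between arms by chance, which moves the count in either direction with no drug effect.

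At stake is the usefulness of the Holter table. It is the planned place to see AF that caused no symptoms and was never reported as an event. As specified, its AF count cannot show whether such AF is new.

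**Working it through.** The plan gives no figure for AF at entry or for new AF, so there is nothing of its own to reproduce on this point. The one design figure, 96% power for the primary endpoint, reproduces (97.4% pooled, 96.3% with continuity correction) but has no bearing here.

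**Inputs.** From SAP 5: 110 subjects per arm. Assumed: a number k per arm in AF at entry, equal in both arms and always counted as AF on Holter; new AF in 6% (mavacamten) versus 2% (placebo) of the 110 − k subjects at risk.

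**Formula.** All-subject percentage = (k + r × (110 − k)) / 110, with r = 0.06 or 0.02.

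Example, k = 11: (11 + 0.06 × 99)/110 = 16.94/110 = 15.4%, and (11 + 0.02 × 99)/110 = 12.98/110 = 11.8%. The ratio is 16.94/12.98 = 1.31 and the difference 3.96/110 = 3.6 points.

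| AF at entry (k per arm) | All-subject count, 6% vs 2% new AF | Ratio | Difference (points) | Ratio among those at risk |
|---|---|---|---|---|
| 0% (0) | 6.0% vs 2.0% | 3.0 | 4.0 | 3.0 |
| 5% (6) | 11.1% vs 7.3% | 1.51 | 3.8 | 3.0 |
| 10% (11) | 15.4% vs 11.8% | 1.31 | 3.6 | 3.0 |
| 15% (16) | 19.7% vs 16.3% | 1.21 | 3.4 | 3.0 |
| 20% (22) | 24.8% vs 21.6% | 1.15 | 3.2 | 3.0 |

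**Chance imbalance.** Suppose 22 of 220 are in AF at entry. The number X falling in one arm is hypergeometric with variance 22 × 0.5 × 0.5 × 198/219 = 4.97. The between-arm difference is 2X − 22, with SD 2 × √4.97 = 4.46. Placebo has at least 4 more such subjects with probability P(X ≤ 9 in the mavacamten arm) = 0.25. The expected excess of new cases is 5.94 − 1.98 = 3.96, so an imbalance of that size would cancel it. With 11 or 44 of 220 in AF at entry the probability is 0.11 or 0.31.

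**AF time.** Assume further that AF at entry fills the whole recording and new AF fills 10% of it. Mean AF time is 0.6% versus 0.2% with nobody in AF at entry, and 10.5% versus 10.2% (SD about 30) with 10% in AF at entry. The raw mean is swamped. Change from the Screening recording is not, because a subject in permanent AF contributes about zero change.

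**The case against.** A reader might infer that participants already in AF mask the stated safety endpoint. The documents do not support that. The endpoint is limited by its own definition to AF/flutter that is new, and it is adjudicated from source documents (Protocol 4.2.2 and 9.3). SAP 10.1 also summarizes and lists AF and flutter adverse events by medical history. Protocol 9.3.4 gives the Holter an exploratory purpose, and nothing says that 10.5 delivers the AF endpoint.

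Three further points on that side stand:

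- The Holter is not the only investigator-independent rhythm source. ECGs go to a central laboratory (Protocol 9.3.3), and ICD data are downloaded at baseline, Week 12 and Week 30 (Protocol 4).
- AF time is largely covered. SAP 6 provides, in general, change-from-baseline summaries for continuous variables, and results are shown by visit. A chance split of 8 versus 14 participants in AF at entry would be visible in the Screening row (8/110 = 7.3% versus 14/110 = 12.7%).
- For an incidence count of new AF, keeping people not at risk in the denominator does little harm: 6/110 versus 2/110 has the same ratio of 3.0 as 6/99 versus 2/99, and the difference is 3.6 instead of 4.0 points. The dilution arises only where existing AF enters the numerator.

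It would also be wrong to infer that adjudicated new AF is never tabulated, since parts of the SAP are blacked out.

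What these points do not answer is the occurrence count itself. A change-from-baseline rule for continuous variables does not reach a yes/no count. A Screening row gives totals, not who converted: a subject with AF at Screening and none at Week 12 offsets a new case. Adjudication works from coded events submitted to the committee, and no readable text says that AF seen only on Holter is submitted.

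**Conclusion.** The point holds for the Holter occurrence count and goes no further. As written, that count cannot separate new from existing AF, and the baseline rule to which SAP 6 refers is missing from 10.5. That the count covers everyone follows from the SAP's default population and denominator rules; 10.5 does not say so itself.

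Under the stated assumptions, a threefold difference in new AF would appear as a ratio of about 1.5 to 1.15. The absolute difference is much better preserved, at 3.8 to 3.2 points instead of 4.0, so the table is blurred and not empty. Every AF rate used is an assumption, and with few participants in AF at entry the effect would be small.

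This is a minor but free improvement to a descriptive safety table. It does not touch the primary analysis or the adjudicated AF endpoint. It also fits the SAP's own practice: ECG results are split by pacing and baseline QRS (10.2), and liver-test normalization takes account of baseline (10.3.1).

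**What to change.** Add one paragraph to SAP 10.5:

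1. Define baseline AF from medical history, the Screening or Day 1 ECG, and the Screening Holter. Name the ECG to be used, because Protocol Table 1 schedules one on Day 1 while Protocol 9.3.3 excepts that visit.
2. Report new on-treatment Holter AF, by arm and visit, among subjects without baseline AF, with the number of such subjects as the denominator.
3. Show AF time and its change from the Screening recording separately for subjects with and without baseline AF.
4. Keep the all-subject table as supportive.

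The cost is one paragraph and one restricted table, plus a split of the AF-time summary. All the data are already scheduled, there is no added burden on participants, and no error-rate question arises because the safety analyses are descriptive.
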